5.2.6.1.2 Serious adverse event

A serious adverse event (SAE) is defined as any AE, which fulfils at least one of the following criteria:

- results in death,
- is life-threatening, which refers to an event in which the patient was at risk of death at the time of the event; it does not refer to an event that hypothetically might have caused death if more severe,
- requires inpatient hospitalisation or prolongation of existing hospitalisation
- results in persistent or significant disability or incapacity,
- is a congenital anomaly / birth defect,
- is deemed serious for any other reason if it is an important medical event when based on appropriate medical judgement which may jeopardise the patient and may require medical or surgical intervention to prevent one of the other outcomes listed in the above definitions. Examples of such events are intensive treatment in an emergency room or at home for allergic bronchospasm, blood dyscrasias or convulsions that do not result in hospitalisation or development of dependency or abuse.

For Japan only: the following events will be handled as “deemed serious for any other reason”. AEs which possibly lead to disability will be reported as SAEs.

5.2.6.1.3 AEs considered “Always Serious”

In accordance with the European Medicines Agency initiative on Important Medical Events, Boehringer Ingelheim has set up a list of further AEs, which by their nature, can always be considered to be “serious” even though they may not have met the criteria of an SAE as defined above.

The latest list of “Always Serious AEs” can be found in the eDC system. A copy of the latest list of “Always Serious AEs” will be provided upon request. These events should always be reported as SAEs as described above.

Cancers of new histology and exacerbations of existing cancer must be classified as a serious event regardless of the time since discontinuation of the drug and must be reported as described in [Section 5.2.6.2](#), subsections “AE Collection” and “**AE reporting to sponsor and timelines**”.

5.2.6.1.4 Adverse events of special interest

The term adverse events of special interest (AESI) relates to any specific AE that has been identified at the project level as being of particular concern for prospective safety monitoring and safety assessment within this trial, e.g. the potential for AEs based on knowledge from other compounds in the same class. AESIs need to be reported to the sponsor’s Pharmacovigilance Department within the same timeframe that applies to SAEs, please see [Section 5.2.6.2.2](#).

The following are considered as AESIs:

Systemic hypersensitivity reactions including anaphylactic reaction

Any suspicion of severe systemic hypersensitivity reaction and of any potential cases of anaphylaxis should be defined and assessed using the criteria discussed in the statement paper from Sampson HA ([Appendix 10.1, R11-4890](#)).

Severe infections (according to RCTC grading in [Appendix 10.2](#))

Opportunistic and mycobacterium tuberculosis infections

These include pneumocystis jirovecii, BK virus disease including PVAN, CMV, post-transplant lymphoproliferative disorder (EBV), progressive multifocal leucoencephalopathy, bartonellosis (disseminated only), blastomycosis, toxoplasmosis, coccidioidomycosis, histoplasmosis, aspergillosis (invasive only), candidiasis (invasive or pharyngeal), cryptococcosis, other invasive fungi (mucormycosis (zygomycosis, rhizopus, mucor, lichtheimia), scedosporium/pseudallescheria boydii, fusarium), legionellosis, listeria monocytogenes (invasive only), tuberculosis, nocardiosis, non-tuberculous mycobacterium, salmonellosis (invasive only), HBV reactivation, herpes simplex (invasive only), herpes zoster, strongyloides (hyperinfection syndrome and disseminated forms only), paracoccidioides, penicillium marneffeii, sporothrix schenckii, cryptosporidium species (chronic only), microsporidiosis, leishmaniasis (visceral only), trypanosoma cruzi infection (Chagas’ disease) (disseminated only), campylobacteriosis (invasive only), shigellosis (invasive only), vibriosis (invasive due to vibrio vulnificus), HCV progression [[R17-2617](#)].

Hepatic injury

A hepatic injury is defined by the following alterations of hepatic laboratory parameters:

- an elevation of AST (Aspartate Aminotransferase) and/or ALT (Alanine Aminotransferase) ≥ 3 fold ULN combined with an elevation of total bilirubin ≥ 2 fold ULN measured in the same blood draw sample, or
- aminotransferase (ALT, and/or AST) elevations ≥ 10 fold ULN.

These lab findings constitute a hepatic injury alert and the patients showing these lab abnormalities need to be followed up according to the “DILI checklist” provided in the ISF.

In case of clinical symptoms of hepatic injury (icterus, unexplained encephalopathy, unexplained coagulopathy, right upper quadrant abdominal pain, etc.) without lab results (ALT, AST, total bilirubin) available, the investigator should make sure these parameters are analysed, if necessary in an unscheduled blood test. Should the results meet the criteria of hepatic injury alert, the procedures described in the DILI checklist should be followed.

5.2.6.1.5 Intensity (severity) of AEs

The intensity grading of AEs will be performed according to Rheumatology Common Toxicity Criteria (RCTC) Version 2.0 developed by OMERACT [[R13-3515](#)]. Refer to the ISF for intensity/severity classification. Intensity options are:

Grade 1	mild
Grade 2	moderate
Grade 3	severe
Grade 4	life-threatening

5.2.6.1.6 Causal relationship of AEs

Medical judgement should be used to determine whether there is a reasonable possibility of a causal relationship between the adverse event and the given study treatment, considering all relevant factors, including pattern of reaction, temporal relationship, de-challenge or re-challenge, confounding factors such as concomitant medication, concomitant diseases and relevant history.

Arguments that may suggest that there is a reasonable possibility of a causal relationship could be:

- The event is consistent with the known pharmacology of the drug.
- The event is known to be caused by or attributed to the drug class.
- A plausible time to onset of the event relative to the time of drug exposure.
- Evidence that the event is reproducible when the drug is re-introduced.
- No medically sound alternative aetiologies that could explain the event (e.g. pre-existing or concomitant diseases, or co-medications).
- The event is typically drug-related and infrequent in the general population not exposed to drugs (e.g. Stevens-Johnson syndrome).
- An indication of dose-response (i.e. greater effect size if the dose is increased, smaller effect size if dose is reduced).

Arguments that may suggest that there is no reasonable possibility of a causal relationship could be:

- No plausible time to onset of the event relative to the time of drug exposure is evident (e.g. pre-treatment cases, diagnosis of cancer or chronic disease within days / weeks of drug administration; an allergic reaction weeks after discontinuation of the drug concerned).
- Continuation of the event despite the withdrawal of the medication, taking into account the pharmacological properties of the compound (e.g. after 5 half-lives).
- Of note, this criterion may not be applicable to events whose time course is prolonged despite removing the original trigger.
- Additional arguments amongst those stated before, like alternative explanation (e.g. situations where other drugs or underlying diseases appear to provide a more likely explanation for the observed event than the drug concerned).
- Disappearance of the event even though the trial drug treatment continues or remains unchanged.

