1.2 DRUG PROFILE

Mode of action

BI 655130 is a humanized antagonistic monoclonal IgG1 antibody that blocks human IL36R signalling. Binding of BI 655130 to IL36R is anticipated to prevent the subsequent activation of IL36R by cognate ligands (IL36 α , β and γ) and downstream activation of pro-inflammatory and pro-fibrotic pathways with the aim to reduce epithelial cell/ fibroblast/ immune cell-mediated inflammation and interrupt the inflammatory response that drives pathogenic cytokine production in inflammatory skin diseases including generalized pustular psoriasis (GPP), palmoplantar pustulosis (PPP) and atopic dermatitis, and inflammatory bowel disease (IBD).

Key pharmacokinetic characteristics

PK analysis showed that exposure (AUC_{0-tz} and C_{max}) to BI 655130 increased with increasing dose in an approximately dose-proportional manner from 0.3 to 10 mg/kg. Overall, PK data so far suggests target-mediated drug disposition (TMDD) kinetics for BI 655130. The effective half-life of BI 655130 is approximately 4 weeks in the linear dose range in healthy volunteers and approximately 3 weeks in GPP patients. For details please see the IB.

Drug interactions

There is no information available. A drug interaction study is planned within the ulcerative colitis program.

Residual Effect Period

The Residual Effect Period (REP) of BI 655130 is 16 weeks. This is the period after the last dose with measurable drug levels and/or pharmacodynamic effects still likely to be present. The consideration behind the REP derivation is that the half-life of ~4 weeks for BI 655130 was observed in the healthy volunteer SRD study of 1368.1. However, in the patient trial 1368.11 where BI 655130 was tested in GPP patients, the effective half-life was 23.9 days, ie. ~3.4 weeks. Therefore 16 weeks would correspond to approximately 5 half-lives in patients, after which time most drug will have been cleared and only less than 3.125% of BI 655130 will still be available.

Data from non-clinical studies

Preclinical studies

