4.2 OTHER TREATMENTS, EMERGENCY PROCEDURES, RESTRICTIONS

4.2.1 Other treatments and emergency procedures

Systemic hypersensitivity including anaphylactic reaction

In case of systemic hypersensitivity including anaphylactic reaction emerging during or after injection(s) of trial medication, the investigator should consider in accordance with severity of the reaction and local standard of care to

- Stop further injection(s)

- Treat with systemic anti-histamines, i.v. steroids, and in case of a severe allergic reaction (e.g., anaphylactic reaction) epinephrine

Also draw a plasma sample for IgE and ADA as detailed in the laboratory manual (ISF) and consider the evaluation of histamine, serum tryptase, and complement components.

In case of systemic hypersensitivity, based on patient's clinical course and medical judgment, injections may be cautiously re-initiated or continued in case of mild or moderate systemic hypersensitivity (according to RCTC grading, provided in the ISF).

In case of anaphylactic reaction based on the criteria discussed in the statement paper from Sampson HA ([Appendix 10.2, R11-4890](#)) suspected to be caused by the trial medication, the investigator should discontinue treatment with study drug.

When a non-acute hypersensitivity reaction related to immune complexes (i.e., serum sickness) is suspected, please draw a sample for the laboratory assessment for circulating immune complexes.

Severe infections (according to RCTC grading in [Appendix 10.3](#)), serious infections, opportunistic or mycobacterium tuberculosis infection

Treatment of the infection should be initiated promptly according to local standard of care. No further trial medication should be administered until the active infection has resolved. Treatment with study drug may be restarted when the patient has recovered according to investigator's assessment.

Malignancies

In case of occurrence of malignant neoplasm other than appropriately treated basal cell carcinoma or squamous cell carcinoma of the skin or in situ carcinoma of uterine cervix, the investigator should discontinue treatment with study drug. Diagnostics and treatment have to be initiated according to local standard of care.

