5.2.6.2 Adverse event collection and reporting

5.2.6.2.1 AE Collection

The investigator shall maintain and keep detailed records of all AEs in the patient files. The following must be collected and documented on the appropriate CRF(s) by the investigator:

- From signing the informed consent onwards until the individual patient's end of trial: all AEs (serious and non-serious) and all AESIs.
- After the individual patient's end of trial: the investigator does not need to actively monitor the patient for new AEs but should only report any occurrence of cancer and trial treatment related SAEs and trial treatment related AESIs of which the investigator may become aware of by any means of communication, e.g. phone call. Those AEs should be reported on the BI SAE form (see Section 5.2.6.2.2), but not on the CRF.

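### The causality guidance uses an allergic reaction weeks after stopping as its example of implausible onset, which does not fit the protocol's own half-life and 16-week residual effect period

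*Protocol*

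**What the plan says.** Protocol Section 5.2.6.1.6 first puts the decision in the investigator's hands, in a sentence that begins: "Medical judgement should be used to determine whether there is a reasonable possibility of a causal relationship between the adverse event and the given study". It then gives two lists. The second is headed "Arguments that may suggest that there is no reasonable possibility of a causal relationship could be". Its first item is the lack of a plausible time to onset relative to exposure, and one of the examples is "an allergic reaction weeks after discontinuation of the drug concerned". The next item concerns an event that continues after withdrawal, and only there is the assessor told to do so "taking into account the pharmacological properties of the compound (e.g. after 5 half-lives").

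Elsewhere the protocol describes a long-lived drug. Section 1.2 gives the effective half-life as "approximately 4 weeks in the linear dose range in healthy volunteers and approximately 3 weeks in GPP patients", with 23.9 days as the exact figure in the GPP trial. It sets the residual effect period at 16 weeks and defines it: "This is the period after the last dose with measurable drug levels and/or pharmacodynamic effects still likely to be present". Section 7.2.5 uses the same 16 weeks to define treatment-emergent events, and SAP Table 6.1: 1 uses the equivalent 112 days. Section 4.2.1 tells the site to draw a further sample "When a non-acute hypersensitivity reaction related to immune complexes (i.e., serum sickness) is suspected". Section 5.2.6.1.4 makes systemic hypersensitivity an AESI.

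**The concern.** An example that suits a short-lived drug has been applied to an antibody with a half-life of 3.4 to 4 weeks. Weeks that the analysis counts as on-drug are the weeks in which an investigator is shown an allergic reaction as a case of implausible timing. No text in the section adapts the example. The 5-half-lives wording does not cure it, because it governs how long an event persists and not when it starts.

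The risk is under-attribution in an event class that the protocol singles out for prospective monitoring. An investigator who follows the example would be nudged towards a not-related judgement for late hypersensitivity. That judgement feeds the drug-related tables, in a trial meant to define a dose range on safety as well as efficacy.

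**Working it through.** **1. The protocol's own figure.** Section 1.2 equates 16 weeks with approximately five half-lives in patients and says that less than 3.125% of the drug then remains. The formula is: fraction left = 0.5^(days / half-life).

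- Five half-lives exactly: 0.5^5 = 3.125%.
- 16 weeks = 112 days. At 23.9 days: 112 / 23.9 = 4.69 half-lives, leaving 3.9%.
- At 28 days: 112 / 28 = 4.0 half-lives, leaving 6.25%.
- At the rounded 3 weeks (21 days): 112 / 21 = 5.33 half-lives, leaving 2.5%.

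The stated bound needs a half-life of 112 / 5 = 22.4 days or less, so it is not reproduced with 23.9 days. This is a separate, small point. Its direction is that slightly more drug remains at 16 weeks than stated.

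**2. Drug left in the weeks that the example covers.** Same formula, time counted from the last dose:

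| Weeks after last dose | Half-life 23.9 days | Half-life 28 days |
|---|---|---|
| 2 | 66.6% | 70.7% |
| 4 | 44.4% | 50.0% |
| 8 | 19.7% | 25.0% |
| 12 | 8.7% | 12.5% |
| 16 | 3.9% | 6.25% |

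If discontinuation is recorded at a visit 4 weeks after the last injection, then 4 weeks after discontinuation is 8 weeks after the last dose, and the 8-week row applies. Section 1.2 also reports that, after four weekly intravenous doses in volunteers, more than 90% of peripheral receptor stayed engaged for at least 22 weeks. The route and doses differ, so this is supportive only.

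**3. Where relatedness is used.**

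- Not used: collection of all AEs and AESIs up to the patient's end of trial (Protocol 5.2.6.2.1); 24-hour notification of SAEs and AESIs (Protocol 5.2.6.2.2); the treatment-emergent definition (Protocol 7.2.5); the AESI table and the hypersensitivity, angioedema and anaphylaxis SMQ searches (SAP 7.8.1).
- Used: the tabulation of causal relationship (Protocol 7.2.5), and the separate drug-related AE and drug-related SAE summaries (SAP 7.8.1).
- Used after the end of trial: the investigator "should only report any occurrence of cancer and trial treatment related SAEs and trial treatment related AESIs" that come to notice (Protocol 5.2.6.2.1).

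**4. When the post-trial filter starts.** Completers reach end of trial at Week 68, which is 68 − 52 = 16 weeks after the last dose. Early discontinuers have the EOS visit 16 weeks after their EOT visit (Protocol 3.3.4.1 and 6.2.3). For both, the filter starts no earlier than the end of the residual effect period. Patients who enter the open-label extension have an earlier individual end of study (SAP Table 6.7: 1), but that is their first dose in the extension, so they have not discontinued the drug. The filter therefore meets the example inside the 16 weeks only for patients who leave follow-up early, for instance by withdrawing consent.

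**The case against.** The strongest reply is that this is one example in a hedged list, subordinate to medical judgement. Its parent criterion refers to time relative to exposure, which a careful reader would interpret through the half-life. Sites are also told that any biologic can provoke immune reactions (Protocol 1.4.2) and are prompted to investigate non-acute ones. The sponsor receives every reported hypersensitivity AESI during the trial whatever its attribution, and the DMC sees unblinded safety data. Residual drug percentages are not counts of misclassified events, and the documents do not link concentration to the onset of allergy. All of this stands and limits the consequence. It does not remove the conflict between the example and the protocol's pharmacology.

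Four stronger readings are tempting, and the documents do not support them.

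- A reader might infer that a not-related judgement by itself takes an event out of expedited reporting. Protocol Section 8.4 says only that the sponsor meets its legal obligations. Neither document says whose assessment decides.
- A reader might infer that late reactions generally go unreported after the trial. Step 4 of the working shows that, within the residual effect period, the filter reaches only patients who leave follow-up early.
- A reader might infer that the error lowers apparent risk only in the active arms. Investigators are blinded, so the same guidance can lower drug-related counts under placebo too.
- A reader might argue from doses always 4 or 8 weeks apart that a reaction at 3 weeks is on-drug before a next dose but implausible after a last one. The flow chart shows weekly administration up to Week 4, so that comparison fits the maintenance phase only.

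**Conclusion.** The point holds as an internal inconsistency with a limited reach. The example points against causality at times when, by the protocol's own half-lives, about 44–50% of the drug is left (4 weeks) or 20–25% (8 weeks), and inside a window that the protocol treats as on-drug. It is a misleading illustration and not a binding rule. It touches the investigator-judged drug-related AE and SAE summaries and, for patients who leave follow-up less than 16 weeks after the last dose, the post-trial reporting. Total TEAE, AESI and SMQ-based counts are unaffected, as are the efficacy analysis, alpha and sample size.

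The percentages assume first-order decline from the last dose. They ignore continuing subcutaneous absorption, and also the target-mediated disposition that Section 1.2 reports, which could change the later part of the curve. The half-lives come from volunteers and GPP patients, not PPP patients. The number of events affected cannot be derived from the documents.

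**What to change.** In Protocol Section 5.2.6.1.6, delete the example or reconcile it with the 16-week residual effect period in Sections 1.2 and 7.2.5 and with the provision for non-acute hypersensitivity in Section 4.2.1. Add that onset within the residual effect period is not in itself an argument against a causal relationship. Carry the same sentence into site training.

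The cost is about one sentence of protocol text and a short training note. No endpoint, sample size, dosing or analysis changes. The downside is that a few more events, in any arm including placebo, may be labelled drug-related.

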5.2.6.2 Adverse event collection and reporting

5.2.6.2.1 AE Collection

The investigator shall maintain and keep detailed records of all AEs in the patient files. The following must be collected and documented on the appropriate CRF(s) by the investigator:

- From signing the informed consent onwards until the individual patient's end of trial: all AEs (serious and non-serious) and all AESIs.
- After the individual patient's end of trial: the investigator does not need to actively monitor the patient for new AEs but should only report any occurrence of cancer and trial treatment related SAEs and trial treatment related AESIs of which the investigator may become aware of by any means of communication, e.g. phone call. Those AEs should be reported on the BI SAE form (see Section 5.2.6.2.2), but not on the CRF.

5.2.6.2.2 AE reporting to the sponsor and timelines

The investigator must report SAEs, AESIs, and non-serious AEs which are relevant for the reported SAE or AESI, on the BI SAE form via fax immediately (within 24 hours) to the sponsor's unique entry point (country specific contact details will be provided in the ISF). The same timeline applies if follow-up information becomes available. In specific occasions, the investigator could inform the sponsor upfront via telephone. This does not replace the requirement to complete and fax the BI SAE form.

With receipt of any further information to these events, a follow-up SAE form has to be provided. For follow-up information the same rules and timeline apply as for initial information. All (S)AEs, including those persisting after individual patient's end of trial must be followed up until they have resolved, have been assessed as "chronic" or "stable", or no further information can be obtained.

[figure not shown]
[figure not shown]
[figure not shown]
5.2.6.2.3 Pregnancy

In rare cases, pregnancy might occur in a clinical trial. Once a patient has been enrolled in the clinical trial and has taken trial medication, the investigator must report any drug exposure during pregnancy in a trial participant immediately (within 24 hours) by means of Part A of the Pregnancy Monitoring Form to the sponsor's unique entry point.

The outcome of the pregnancy associated with the drug exposure during pregnancy must be followed up and reported to the sponsor's unique entry point on the Pregnancy Monitoring Form for Clinical Trials (Part B).

The ISF will contain the Pregnancy Monitoring Form for Clinical Trials (Part A and B).

As pregnancy itself is not to be reported as an AE, in the absence of an accompanying SAE and/or AESI, only the Pregnancy Monitoring Form for Clinical Trials and not the SAE form is to be completed. If there is an SAE and/or AESI associated with the pregnancy an SAE form must be completed in addition.

